Subjects should be seen for all visits/assessments as outlined in the assessment schedule or as close to the designated day/time as possible. Missed or rescheduled visits should not lead to automatic discontinuation. Subjects who prematurely discontinue the study for any reason should be scheduled for a visit as soon as possible, at which time all of the assessments listed for the final End of Treatment (EOT) visit will be performed. At this final visit, all dispensed investigational product should be reconciled, and the adverse event and concomitant medications recorded on the CRF.

Study treatment will begin on Cycle 1 Day 1 (C1D1) with the first administration of the assigned study treatment, depending on the arm into which the subject has been allocated (Part 1) or randomized (Parts 2 and 3). C1D1 should occur on the same day as the allocation/randomization to study treatment, however if this is not logistically possible, it should not be more than 3 days after allocation/randomization in IRT. Each treatment cycle is 21 days for all treatment arms containing NIS793 or 28 days for all other treatment arms. It is recommended that a 28-day gap between Cycle (X) Day 1 and Cycle (X+1) Day 1 is maintained in ruxolitinib + siremadlin combination arm. The duration between cycles should not be shortened to < 28 days due to potential for additive hematotoxicity and adequate time for bone marrow recovery between cycles.

All study visits, assessments and study treatment administration are to be scheduled according to the appropriate number of calendar days from the day of first study treatment administration on C1D1 (whenever possible as per the allowable visit window specified in Table 8-1 below). If one of the investigational drugs is interrupted or permanently discontinued, at any time during the study, all study visits and safety assessments should continue according to the appropriate number of calendar days from C1D1 as per the schedule of assessments, and efficacy assessments must continue as per the scheduled number of weeks from C1D1 as described in

Table 8-2 (Part 1) and Table 8-3 (Parts 2 and 3) for treatment arms with 28-day cycles (all treatment arms not containing NIS793 except the monotherapy arm in Part 3 if ruxolitinib + NIS793 is chosen for Part 3), and Table 8-4 (Part 1) and Table 8-5 (Parts 2 and 3) for treatment arms containing NIS793.

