Every effort must be made to follow the schedule of assessments within the windows outlined in the protocol.

Study visits with scheduled PK sampling should be scheduled in the morning so that a pre-dose PK blood sample can be collected.

The preferred sequence for assessments during study visits is ECG collection first, followed by vital signs, and blood sampling.

For Japan only, subjects enrolled in the crizanlizumab arm of Part 1 (Arm 2) are required to be hospitalized in the first 7 days of study treatment.

As per Section 4.6, during a Public Health emergency as declared by Local or Regional authorities i.e. pandemic, epidemic or natural disaster that limits or prevents on-site study visits, alternative methods of providing continuing care may be implemented by the investigator as the situation dictates. If allowed by local Health Authority and depending on operational capabilities, phone calls, virtual contacts (e.g. tele consult) or visits by site staff/ home nursing staff to the participant's home, can replace on-site study visits, for the duration of the disruption until it is safe for the participant to visit the site again.

Table 8-1 Allowable visit windows

Visit name	Assessments	Window allowed
Screening	MRI/CT scan of abdomen (all parts)	within 8 weeks prior to first dose of study treatment
	Cardiac imaging (MUGA or echocardiogram or cardiac MRI) and ophthalmologic exams (Part1 only)	≤ 28 days before C1D1
	Bone marrow biopsy (part 2 and 3)	within 8 weeks prior to first dose of study treatment
	All other assessments	≤ 28 days before C1D1
C1D1	IRT dispensing call	-3 days
(Core Phase)	Cardiac imaging (MUGA or echocardiogram or cardiac MRI) and ophthalmologic exams (Part 2 and Part 3)	-3 days
	All other visit assessments and administration of study drugs	NA
Day 1 visit of all subsequent cycles	Cardiac imaging and ophthalmologic exams	-7 days
(Core and extension)	All other visit assessments and administration of study drugs	± 3 days
During Treatment and Safety Follow-up periods	PK sampling	Refer to PK sample tables in Section 8.5.2
EOT Core Phase for subjects not entering in extension;	All assessments	+ 7 days after last dose of study treatment (except for MRI/CT scan or bone marrow biopsy if completed in
EOT extension		the past 12 weeks)
EOT core for subjects entering in extension	All assessments	± 3 days (EOT core and C1D1 extension visits
and C1 D1 (extension)		must be performed on the same day)

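### For siremadlin, the ± 3-day dosing window in Table 8-1 permits Day 1 doses 22 days apart, while Section 8 says cycles should not be shorter than 28 days

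*Protocol*

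**What the plan says.** Three statements bear on the spacing of siremadlin cycles, all in Protocol Section 8 (Visit schedule and assessments).

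- **Cycle length and minimum gap.** The general rule is "Each treatment cycle is 21 days for all treatment arms containing NIS793 or 28 days for all other treatment arms". For siremadlin the text adds "It is recommended that a 28-day gap between Cycle (X) Day 1 and Cycle (X+1) Day 1 is maintained in ruxolitinib + siremadlin combination arm", and then "The duration between cycles should not be shortened to < 28 days due to potential for additive hematotoxicity". The second stated reason is time for the bone marrow to recover.
- **Anchor.** The following paragraph says that visits, assessments and dosing "are to be scheduled according to the appropriate number of calendar days from the day of first study treatment administration on C1D1", with the qualifier "whenever possible as per the allowable visit window specified in Table 8-1 below". The reference point is C1D1, not the date on which the previous cycle was actually dosed.
- **Window.** Table 8-1 has a row for "Day 1 visit of all subsequent cycles", marked as covering both core and extension phases. In it, the entry "All other visit assessments and administration of study drugs" carries ± 3 days. The matching entry for C1D1 of the core phase is NA, so the first dose has no window. No row or footnote sets siremadlin apart.

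Siremadlin is taken on Days 1 to 5 of each 28-day cycle (Section 6.7.2.2).

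**The concern.** A site that follows Table 8-1 to the letter can dose siremadlin at an interval that the opening text of Section 8 says should not be used. The table covers drug administration as well as assessments, so this is not only a question of visit timing. Because the calendar runs from C1D1, a late dose does not move the next due date. A return to the calendar after a late dose therefore shortens the following gap.

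Two things are at stake. The first is the safety purpose of the 28-day text, which rests on hematotoxicity and marrow recovery, for subjects still taking siremadlin in the extension phase. The second is classification. SAP Section 2.3.1 tabulates and lists protocol deviations, and Protocol Section 14 asks investigators to avoid them. The same interval is compliant by the table and contrary to the text, so two sites could record it differently.

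**Working it through.** **Inputs**

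- Planned cycle length 28 days, and a minimum Day 1 to Day 1 gap of 28 days for siremadlin (Section 8).
- Scheduling by calendar days from C1D1 (Section 8).
- Dosing window: none at C1D1, and -3 to +3 days on Day 1 of Cycle 2 onward (Table 8-1).
- Five siremadlin dosing days per cycle (Section 6.7.2.2).

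**Formulas.** The nominal Day 1 of cycle k is 1 + 28(k - 1). Write o(k) for the offset actually used, with o(1) = 0 and o(k) between -3 and +3 for k of 2 or more. Then:

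- gap from cycle k to k+1 = 28 + o(k+1) - o(k)
- siremadlin-free days = gap - 5

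**The plan's own figure.** With all offsets zero, Day 1 falls on study days 1, 29, 57, 85, 113 and 141. Every gap is 28 days, with 28 - 5 = 23 siremadlin-free days. Six cycles take 6 × 28 = 168 days, or 24 weeks, which agrees with Section 6.1.5. The 28-day figure therefore reproduces on the nominal schedule.

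**With the window applied**

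| Pair | Offsets | Gap (days) | Siremadlin-free days |
|---|---|---|---|
| C1 to C2, shortest | 0, then -3 | 28 - 3 = 25 | 20 |
| C2 to C3 and later, shortest | +3, then -3 | 28 - 3 - 3 = 22 | 17 |
| C2 to C3 and later | +3, then 0 | 28 - 3 = 25 | 20 |
| C2 to C3 and later | +1, then 0 | 28 - 1 = 27 | 22 |
| C2 to C3 and later, longest | -3, then +3 | 28 + 3 + 3 = 34 | 29 |

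In dates, the 22-day case is Cycle 2 on day 29 + 3 = 32 and Cycle 3 on day 57 - 3 = 54. An in-window run of Day 1 doses on days 1, 32, 54, 88, 110 and 144 has gaps of 31, 22, 34, 22 and 34 days.

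**How many permitted combinations fall below 28 days.** A gap is below 28 whenever the next offset is smaller than the current one. From Cycle 2 onward that is (49 - 7)/2 = 21 of the 7 × 7 = 49 offset pairs. For C1 to C2 it is 3 of 7. These count what the table allows. They are not probabilities.

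**Sensitivity to the anchor.** If the window were counted from the previous actual dose instead of from C1D1, the shortest gap would be 28 - 3 = 25 days. The conflict with 28 days does not depend on the anchor. Only the 22-day figure does.

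**The case against.** The best reply is that the two texts can be followed together. Table 8-1 is general to all arms, while the 28-day text is specific to siremadlin and was written in the same Amendment 8 revision that updated the window table. A specific limit would normally narrow a general window. The text is also soft (recommended, should not). A 22-day gap needs +3 followed at once by -3, and it can only follow a dose already 3 days behind the calendar. The siremadlin dose-modification tables are not visible in the public copy, so another safeguard cannot be excluded. Table 6-10 already ties restart after severe cytopenia to recovery.

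Part of this stands. Schedules that satisfy both texts exist, and the extreme case is unlikely in practice. But the reply does not settle which text governs. If the 28-day limit prevails, offsets start at zero and may never decrease. The minus side of the printed window is then unusable, total lateness over the core cycles is capped at 3 days, and a subject dosed late cannot return to the C1D1 calendar that Section 8 prescribes. Nothing in Table 8-1 tells a site this. A one-day delay followed by an on-time dose already gives 27 days, so no extreme schedule is needed.

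A reader might also infer that the conflict affected the dose-finding data, through a denser schedule in Cycles 1 and 2 or a mismatch with the BLRM prior. The documents do not support that:

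- The amendment record lists the siremadlin cycle-length recommendation among the Amendment 8 changes to Section 8. Recruitment had then been halted since 17-Jun-2022, and all four ongoing subjects had completed at least six cycles. No subject can pass through the DLT window (C1D1 to C3D1) under this text.
- The prior is not tied to exact four-week spacing. Table 16-4 scales each historical regimen by dose per cycle divided by five, with no adjustment for cycle length. Regimen 1A, a three-week cycle, is treated the same way (50/5 = 10.0; 350/5 = 70.0). Half the prior weight sits on a vague component.

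**Conclusion.** The inconsistency is real, and it lies in the wording of the current protocol. A dosing window that applies to siremadlin permits Day 1 intervals of 22 days from Cycle 2 onward (25 from Cycle 1 to Cycle 2), against a safety-motivated statement that 28 days should not be undercut. No text ranks one above the other.

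Its scale is small. SAP Section 1.1 caps extension entry at 4 subjects, on different combinations and/or dose levels. At Amendment 8 the ongoing subjects were spread over the siremadlin and rineterkib arms, so the siremadlin number may be lower than 4. Each may be treated for up to 21 extension cycles. The documents do not report that any short interval occurred, and none is claimed here.

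The conclusion assumes that the ± 3 days apply to siremadlin as printed, and that no hidden table states an overriding rule.

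**What to change.** Reconcile Section 8 and Table 8-1 for the ruxolitinib + siremadlin arm. One statement, cross-referenced from the other place, should settle three things:

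- which Day 1 to Day 1 intervals are in-window;
- what the next due date is counted from when the previous cycle was dosed late;
- which intervals are recorded as protocol deviations.

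This review takes no position on which interval or window is right. The sponsor has to decide that on clinical grounds.

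The cost is protocol wording and one table entry or footnote, made through a written amendment as Section 14.1 requires. No additional data are needed, and no analysis changes beyond consistent classification of deviations.

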8.1 Screening

The screening period begins once written informed consent is provided and ends after 28 days or when subject is allocated (Part 1) /randomized (Parts 2 and 3) to study treatment, whichever comes first.

Screening assessments to confirm eligibility into the study, as described in Table 8-2 and Table 8-3, Table 8-4 and Table 8-5 should be performed within 1 to 28 days prior to the first dose of study treatment, unless otherwise specified in Table 8-1.

A serum pregnancy test, where applicable, must be confirmed negative prior to the first dose of study treatment.

A subject who has a laboratory test result(s) that does not satisfy the entrance criteria may have the test(s) repeated once, prior to randomization. These test(s) may be repeated as soon as the investigator believes the re-test result(s) is/are likely to be within the acceptable range to satisfy the entrance criteria, but should be completed within approximately 3 weeks of the original screening visit date. In this case, the subject will not be required to sign another ICF, and the original subject ID number assigned by the investigator will be used. In the event that the laboratory test(s) cannot be performed within 3 weeks of the original screening visit, or the retest(s) do not meet the entrance criteria, or other eligibility criteria have changed and are not met anymore, the subject is considered a screen failure.

A new ICF will need to be signed if the investigator chooses to re-screen the subject after a subject has screen failed. A new subject ID number will be used. All required screening activities must be performed when the subject is re-screened for participation in the study to satisfy eligibility requirements. An individual subject may only be re-screened once for the study. Once the number of subjects screened and enrolled is likely to ensure target enrollment, Novartis may close the study to further screening. In this case, the subjects who screen failed will not be permitted to re-screen.

8.1.1 Eligibility screening

Following registering in the IRT for screening, subject eligibility will be checked once all screening procedures are completed. The eligibility check will be embedded in the IRT system. Please refer and comply with detailed guidelines in the IRT manual.

8.1.2 Information to be collected on screening failures

Part 1 subjects who sign an ICF and subsequently found to be ineligible will be considered a screen failure. The reason for screen failure should be entered on the applicable CRF. The demographic information, informed consent, disease diagnosis, prior ruxolitinib treatment, Inclusion/Exclusion pages and study disposition must also be completed for screen failure subjects. No other data will be entered into the clinical database for subjects who are screen failures, unless the subject experienced a serious adverse event during the screening phase (see SAE Section 10.1.2 for reporting details).

Part 1 subjects who sign an informed consent and are considered eligible but fail to be started on treatment for any reason will be considered an early terminator. The reason for early termination should be captured on the appropriate disposition CRF.

Part 2 and Part 3 subjects who sign the study ICF but are subsequently found to be ineligible prior to randomization will be considered a screen failure. The demographic information, informed consent, and Inclusion/Exclusion and study disposition pages must also be completed for screen failure subjects. No other data will be entered into the clinical database for subjects who are screen failures, unless the subject experienced a serious adverse event during the screening phase (see SAE Section 10.1.2 for reporting details). If the subject fails to be randomized, the IRT must be notified within 2 days of the screen fail that the subject was not randomized.

Part 2 and Part 3 subjects who are randomized and fail to start study treatment for any reason will be considered an early terminator. The reason for early termination should be recorded on the appropriate CRF.

8.2 Subject demographics/other baseline characteristics

The following data on subject characteristics will be collected at screening for all Parts of the study as listed in Table 8-2, Table 8-3, Table 8-4 and Table 8-5:

- Demographic information: age at consent, gender, ethnicity and race (if permitted)
- Participant race/ethnicity data are collected and analyzed to identify any difference in the safety and/or efficacy profile of the treatment due to these characteristics. In addition, the diversity of the study population should be taken into consideration to support subgroup analysis as required by some Health Authorities. Relevant medical history (including medical conditions present at time of ICF signature)
- Diagnosis of disease
- Prior ruxolitinib treatment (≥ 12 weeks and on a stable dose ≥ 4 weeks)
- All prior anti-neoplastic therapies (medications, surgeries, radiation)
- Prior and concomitant medications: All medications and significant non-drug therapies taken within 30 days prior to the first dose of study treatment must be recorded in the CRF. They will be updated on a continuous basis if there are any new changes to the medications.
- HIV history (If mandated per local requirements, a local HIV testing is to be done during screening)
- Transfusion record for PRBC and platelets

Subjects will have the following screening assessments performed before the start of study treatment in all Parts of the study as listed in Table 8-2, Table 8-3, Table 8-4 and Table 8-5:

- Physical examination
- Height
- Weight
- Vital signs

- Laboratory assessments Hematology, chemistry, coagulation, urinalysis, thyroid function, Troponin I and NTproBNP for NIS793 patients in Part 1 and all patients in part 2 and 3 if NIS793 is open for enrollment.
- Hepatitis test
- HIV screen (if required per local regulations)
- Serum pregnancy test
- Spleen measurement by palpation
- Baseline MRI/CT (if not already performed within 8 weeks prior to first dose of study treatment)
- PRO questionnaires (MFSAF v4.0 and EORTC QLQ-C30)
- Bone marrow biopsy and aspirate for measuring bone marrow fibrosis changes (Parts 2 and 3)
- ECOG performance status
- **ECG**
- Cardiac imaging as required based on the allocated study treatment.

8.3 **Efficacy**

As the enrollment was permanently halted, the only randomized subject in Part 2 has discontinued prior to this amendment, and Part 3 will not be initiated, therefore the descriptions of endpoints for Parts 2 and 3 are not applicable. Secondary efficacy endpoints for Part 1 are outlined in Table 2-1.

8.3.1 Response rate for the composite primary efficacy endpoint

The primary efficacy endpoint for Part 2 and Part 3 is the response rate (RR) of the composite of the following, assessed at the end of Cycle 8 (for treatment arms with NIS793) or Cycle 6 (for all other treatment arms) Section 12.4.1:

- Improvement in anemia of > 1.5 g/dL, and
- No spleen volume progression, and
- No symptoms worsening

The composite criteria are defined as follows:

- Anemia improvement requires an increase of hemoglobin from baseline of at least 1.5 g/dL
- Spleen volume progression is defined as a spleen volume increase of 25% or more from baseline as determined by MRI/CT
- Symptoms worsening is defined as a total symptom score (TSS) increase of 10 or more from baseline assessed by MFSAF version 4.0

The following assessments will be utilized to determine the 3 components for the RR

Anemia improvement requires an increase of hemoglobin from baseline of at least 1.5 g/dL as measured at the end of Cycle 8 (arms with NIS793) or Cycle 6 (all other arms). The increase in

hemoglobin should be confirmed at least 2 weeks later. Anemia improvement requires the absence of any PRBC transfusion in the 12 weeks prior to achieving an increase of 1.5 g/dL.

Laboratory Hb assessments (as outlined in Section 8.4.1) taken at the end of Cycle 8 (arms with NIS793) or Cycle 6 (all other arms) in comparison to C1D1 will be used to determine those subjects that achieved an improvement of ≥ 1.5 g/dL.

8.3.1.2 Spleen volume progression

Evaluation of spleen volume will be performed by Magnetic Resonance Imaging (MRI) or Computed Tomography (CT) scan. MRI of the spleen (or CT if MRI is contraindicated) will be performed as regular assessment at screening, and at the end of Cycle 8 (arms with NIS793) or Cycle 6 (all other arms) in comparison to the screening assessment (baseline). Previously completed scans can be considered for baseline if obtained within 8 weeks prior to first dose of study treatment (C1D1).

Volumetric spleen size progression is defined as a spleen volume increase of at least 25% from baseline, as per IWG-MRT revised criteria (Tefferi et al 2013).

MRI will be performed with a body coil because the objective is to measure organ volume, not to find very small lesions. MRIs will be performed and assessed by local radiologists who will be instructed to provide a quantitative and a qualitative assessment of spleen volume (as enlarged, smaller, larger, etc.). The MRI will not determine spleen length below the costal margin, as there are no validated approaches for determining this measurement. The site radiologist will provide the read-out and the results from the local evaluations will be used for the endpoints analyses.

MRI is the preferred method for obtaining spleen volume data. However, CT scans may be performed at the visits where MRI would be conducted if the subject is not a candidate for MRI (because of the presence of metal clips in the body, or because of claustrophobia, for example), or if MRI is unavailable to the study site.

Generally, the same method (MRI or CT) should be consistently used for all visits for a given subject unless a new contraindication to the use of MRI (eg, pacemaker insertion) occurs.

Any imaging assessments already completed during the regular work-up of the subject within 8 weeks prior to start of study treatment, including before signing the main study ICF, can be considered as the baseline images for this study. Any imaging assessments obtained after allocation (Part 1)/randomization (Part 2 and Part 3) cannot be considered baseline images.

Imaging assessments during the study should be scheduled using the allocation/randomization date as the reference date and should be respected regardless of whether study treatment is temporarily withheld or unscheduled assessments performed.

Additional imaging assessments may be performed at any time during the study at the investigator's discretion to support the efficacy evaluations for a subject, as necessary. Clinical suspicion of disease progression at any time requires a physical examination and imaging

assessments to be performed promptly rather than waiting for the next scheduled imaging assessment.

Total symptom score (TSS) worsening 8.3.1.3

Symptom worsening occurs when the total symptom score (TSS) assessed by MFSAF v4.0 increases 10 or more scores from baseline (C1D1) at the end of Cycle 8 (arms with NIS793) or Cycle 6 (all other arms). Refer to Section 8.5.1 for a description of the MFSAF v4.0 PRO. The TSS absolute increase of 10 or more from baseline is considered as a clinical meaningful symptom worsening based on the COMFORT I trial data using a combination of distributionand anchor- based approaches (Dueck et al 2017). An absolute score change, rather than a percentage change, is the criterion as the latter would either require not enough change in magnitude for a lower baseline or too much change in magnitude for a higher baseline.

